2 OBJECTIVES

2.1 PRIMARY OBJECTIVE

- To characterize the frequency of bleeding episodes while receiving fitusiran treatment, relative to the frequency of bleeding episodes while receiving factor concentrate or bypassing agent (BPA) prophylaxis. For the United States specific requirements, see [Section 11.6.1.2](#).

2.2 SECONDARY OBJECTIVES

- To characterize the following while receiving fitusiran treatment, relative to receiving factor or BPA prophylaxis (for the United States specific requirements, see [Section 11.6.1.2](#)):
 - the frequency of spontaneous bleeding episodes
 - the frequency of joint bleeding episodes
 - health related quality of life (HRQOL) in patients ≥ 17 years of age
- To characterize the frequency of bleeding episodes during the onset and treatment periods in patients receiving fitusiran
- To characterize safety and tolerability of fitusiran
- To characterize the annualized weight-adjusted consumption of factor/BPA while receiving fitusiran treatment, relative to receiving factor or BPA prophylaxis

2.3 EXPLORATORY OBJECTIVES

- To characterize the effects of fitusiran on the following patient-reported outcomes while receiving fitusiran treatment, relative to receiving factor or BPA prophylaxis (for the United States specific requirements, see [Section 11.6.1.2](#)):
 - Patient satisfaction with fitusiran
 - Patient activity
 - HRQOL in adolescents (≥ 12 to < 17 years of age)
- To characterize the pharmacodynamic (PD) effect, PK, and immunogenicity of fitusiran
- To characterize the effects of fitusiran on joint status while receiving fitusiran treatment, relative to receiving factor or BPA prophylaxis
- To characterize the effects of fitusiran on patient resource use, relative to receiving factor or BPA prophylaxis

3 ENDPOINTS

3.1 PRIMARY ENDPOINT

- Annualized Bleeding Rate (ABR) in the fitusiran efficacy period and the factor or BPA prophylaxis period (for the United States specific requirements, see [Section 11.6.1.2](#))

3.2 SECONDARY ENDPOINTS

- Annualized spontaneous bleeding rate in the fitusiran efficacy period and the factor or BPA prophylaxis period (for the United States specific requirements, see [Section 11.6.1.2](#))
- Annualized joint bleeding rate in the fitusiran efficacy period and the factor or BPA prophylaxis period (for the United States specific requirements, see [Section 11.6.1.2](#))
- Change in Haem-A-QOL physical health score and total score in the fitusiran treatment period and the factor or BPA prophylaxis period
- ABR in the onset period
- ABR in treatment period
- Annualized weight-adjusted consumption of factor/BPA

3.3 EXPLORATORY ENDPOINTS

- Change in the following in the fitusiran treatment period:
 - Treatment Satisfaction Questionnaire for Medication (TSQM) domain scores
 - Haemophilia Activities List (HAL) score
 - Paediatric HAL (pedHAL) score
 - EuroQol-5 Dimensions (EQ-5D) score
 - Haemo-QOL score
 - Hemophilia Joint Health Score (HJHS)
- Number of target joint bleeding episodes
- Incidence and titer of antidrug antibodies to fitusiran in the fitusiran treatment period
- AT activity level over time
- Thrombin generation over time
- Fitusiran plasma levels
- Change in patient resource use (eg, work/school attendance, visits to doctor/hospital)

3.4 SAFETY ENDPOINT

- Incidence, severity, seriousness, and relatedness of adverse events

4 INVESTIGATIONAL PLAN

4.1 SUMMARY OF STUDY DESIGN

The ATLAS-PPX trial (ALN-AT3SC-009) is a multicenter, multinational, open-label, Phase 3 study designed to characterize the efficacy and safety of fitusiran in male patients, aged ≥ 12 years, with severe hemophilia A or B, previously receiving factor or BPA prophylaxis. The study consists of 2 cohorts: Cohort A will consist of patients with inhibitory antibodies to Factor VIII or Factor IX; Cohort B will consist of patients without inhibitor antibodies to Factor VIII or Factor IX. A subgroup of Cohort A patients will include hemophilia B patients with inhibitory antibodies to Factor IX who are not responding adequately to BPA prophylaxis treatment (historical ABR ≥ 20) (see Inclusion Criteria in [Section 5.1](#)). The study has 3 periods defined by type of prophylaxis regimen (for the United States specific requirements, see [Section 11.6.1.2](#)):

- 6-Month factor or BPA prophylaxis period in which patients will continue their prestudy, regularly scheduled prophylaxis regimen with factors or BPAs

The subgroup of Cohort A patients who are not responding adequately to BPA prophylaxis treatment will not participate in this 6-Month BPA prophylaxis period and will start to directly receive fitusiran (in the 1-month onset period described below) after the screening period.

- 1-Month onset period in which patients receive first dose of fitusiran while continuing their factor or BPA prophylaxis for up to 7 days
- 6-Month fitusiran efficacy period in which patients receive fitusiran as prophylaxis.

Together, the 1-month onset period and the 6-month fitusiran efficacy period constitute the fitusiran treatment period.

Bleeding events and doses of factor concentrates or BPAs administered during the conduct of the study will be recorded in an electronic Diary (eDiary), as described in [Section 7.2.1](#). Since bleeding episodes are recorded as an efficacy assessment of fitusiran, these will not be treated as AEs unless they meet any of the SAE criteria listed in [Section 7.6.6.1](#). Safety, quality of life, pharmacodynamic, and pharmacokinetic data will also be collected.

On-demand use of factor concentrates or BPAs is defined as the use of these agents, as needed, for episodic bleeding, and not on a regular regimen intended to prevent spontaneous bleeding. Throughout the study, patients in the fitusiran treatment period may receive on-demand treatment for breakthrough bleeding episodes with factors or BPAs, as appropriate. For patients in the fitusiran treatment period who have received at least 1 dose of fitusiran and are being treated for breakthrough bleeding episodes, it is recommended to follow the guidelines provided in [Section 6.3.2](#) per Investigator discretion.

Following the screening and prophylaxis periods or following the screening period for the subgroup of Cohort A enrolling directly into the fitusiran treatment period all patients will be treated with fitusiran for a total of 7 months. Therefore, the overall fitusiran treatment period is

defined as the onset period (Day 1-28 after receipt of the first dose, during which the AT lowering capacity of fitusiran is increasing but has not yet reached therapeutic levels) plus the efficacy period (Day 29 and after, when the AT lowering capacity of fitusiran has achieved therapeutic target range). For the United States specific requirements, see [Section 11.6.1.2](#).

[figure not shown]
Any current surgery occurring close to the date of the Screening visit must have surgery-related hemostatic treatment completed at least 72 hours prior to Screening. Patients may undergo unplanned or emergency surgery during the study but must not schedule non-urgent surgery to occur during the study. Perioperative guidance should be followed as specified in [Section 6.6](#).

A study Steering Committee, composed of experts in the field of hemophilia, will advise the Sponsor on study design and conduct ([Section 4.6](#)).

An independent data monitoring committee (DMC) will oversee the safety and overall conduct of this study as described in [Section 4.7](#).

The study design schema is presented in [Figure 1](#). Patients who complete the study may be eligible for an open-label extension study.

Figure 1 - Study design

[figure not shown]
Abbreviations: AT=antithrombin

Note: For subgroup of Cohort A patients enrolling directly into the fitusiran treatment period, see [Figure 2](#).

Note: For the United States specific requirements, see [Section 11.6.1.2](#).

^a Patients will continue to receive prescribed factor or BPA prophylaxis for the first 7 days of the onset period.

^b Following final fitusiran dose, AT activity level will be monitored at monthly intervals following the final fitusiran dose until activity levels return to approximately 60% (per the central laboratory) or per Investigator discretion in consultation with the study Medical Monitor.

Figure 2 - Study design (for subgroup of Cohort A patients enrolling directly into the fitusiran treatment period)

Abbreviations: AT=antithrombin

Note: For the United States specific requirements, see [Section 11.6.1.2](#).

a Patients will receive prescribed factor or BPA prophylaxis for the first 7 days of the onset period.

b Following final fitusiran dose, AT activity level will be monitored at monthly intervals following the final fitusiran dose until activity levels return to approximately 60% (per the central laboratory) or per Investigator discretion in consultation with the study Medical Monitor.

4.2 DURATION OF TREATMENT

The duration of treatment with fitusiran is 7 months. The estimated total time on the study, inclusive of screening, for each patient is up to 15 months for all patients who enroll in the extension study, except for patients in the subgroup of Cohort A, which is up to 9 months. The estimated total time on study may be up to 21 months (up to 15 months for patients in the subgroup of Cohort A) for patients who do not enroll in the extension study due to the requirement for an additional 6 months of follow-up for monitoring of AT levels.

4.3 NUMBER OF PATIENTS

Approximately 80 patients are planned for enrollment in this study, including approximately 30 patients with inhibitors (Cohort A) and approximately 50 patients without inhibitors (Cohort B). Approximately 18 patients with hemophilia B (including approximately 7 hemophilia B patients in Cohort A, among which are a subgroup of no more than 4 patients who are not responding adequately to BPA prophylaxis [see [Section 5.1](#)]), approximately 11 hemophilia B patients in Cohort B, and approximately 7 adolescents (≥ 12 to < 18 years of age) are also planned for enrollment. For the United States specific requirements, see [Section 11.6.1.2](#).

4.4 METHOD OF ASSIGNING PATIENTS TO TREATMENT GROUPS

All patients will be assigned to the same treatment sequence (prophylaxis period followed by fitusiran period) in this open-label study.

Each patient will be uniquely identified in the study by a combination of the site number and patient identification number. Upon signing the informed consent form (ICF), the patient will be assigned a patient identification number by the interactive response system (IRS). The Investigator or his/her delegate will contact the IRS after confirming that the patient fulfills all the inclusion criteria and none of the exclusion criteria. A combination of the site number and patient identification number will create the unique patient identifier.

4.5 BLINDING

This study is an open-label study so blinding is not applicable; however, performing aggregate summaries of efficacy data will be restricted until database lock.

4.6 STUDY STEERING COMMITTEE

A study Steering Committee, composed of experts in the field of hemophilia, will advise the Sponsor on study design and conduct. In collaboration with the Sponsor, the committee will provide scientific leadership to the study to ensure that the highest standards are maintained.

Clinical Advisors who are experts in the care of hemophilia patients and familiar with fitusiran will be available to discuss clinical aspects of care with Investigators for surgical cases, cases of thrombosis, or other medically complex circumstances that may arise on study, when clinical circumstances allow. Such discussions will also look to involve the study Medical Monitor.

4.7 DATA MONITORING COMMITTEE

An independent DMC will oversee the safety and overall conduct of this study, providing input to the Sponsor. The DMC will operate under the rules of a charter that will be reviewed and approved at the organizational meeting of the DMC. The DMC has the responsibility for reviewing safety data and analyses and making recommendations to the Sponsor. The DMC will perform periodic reviews of data during the course of the clinical trial, and on an ad hoc basis for review of emergent safety data, as defined in the DMC Charter for this clinical trial.

5 SELECTION AND WITHDRAWAL OF PATIENTS

5.1 INCLUSION CRITERIA

Each patient must meet all of the following inclusion criteria to be eligible for enrollment in the study (for the United States specific requirements, see [Section 11.6.1.2](#)):

- I 01. Males ≥ 12 years of age.
- I 02. Severe hemophilia A or B as evidenced by:
- A central laboratory measurement at screening or documented medical record evidence of FVIII $< 1\%$ or FIX level $\leq 2\%$.
- I 03. A minimum of 2 bleeding episodes requiring BPA treatment within the last 6 months prior to Screening for patients with inhibitory antibodies to Factor VIII or Factor IX (Cohort A). A minimum of 1 bleeding episode requiring factor treatment within the last 12 months prior to Screening for patients without inhibitory antibodies to Factor VIII or Factor IX (Cohort B).
- I 04. Must meet either the definition of inhibitor or non-inhibitor patient as below:

Inhibitor:

Use of BPAs for prophylaxis and for any bleeding episodes for at least the last 6 months prior to Screening, and meet one of the following Nijmegen-modified Bethesda assay results criteria:

- Inhibitor titer of ≥ 0.6 BU/mL at Screening, or
- Inhibitor titer of < 0.6 BU/mL at Screening with medical record evidence of 2 consecutive titers ≥ 0.6 BU/mL, or
- Inhibitor titer of < 0.6 BU/mL at Screening with medical record evidence of anamnestic response
- The subgroup of patients in Cohort A patients must additionally meet the following criteria to be eligible to start treatment with fitusiran directly after the screening period:
 - Hemophilia B with inhibitory antibody to Factor IX as defined above
 - Not responding adequately to BPA treatment (historical ABR ≥ 20) prior to enrollment
 - In the opinion of the Investigator, with approval of Sponsor Medical Monitor, 6-month BPA prophylaxis period should be omitted.

Non-inhibitor:

Use of factor concentrates for prophylaxis and for any bleeding episodes for at least the last 6 months prior to Screening, and meet each of the following criterion:

- Nijmegen-modified Bethesda assay inhibitor titer of <0.6 BU/mL at Screening and
 - No use of bypassing agents to treat bleeding episodes for at least the last 6 months prior to Screening and
 - No history of immune tolerance induction therapy within the past 3 years prior to Screening.
- I 05. Prescribed prophylactic treatment (documented in the medical or pharmacy records) of hemophilia with factor concentrates or BPAs for at least 6 months prior to Screening; the regimen must be consistent with the approved prescribing information for the product or local recommendations, allowing for adjustment to individual patient response, and designed to decrease spontaneous bleeding.
- I 06. Adherent to the prescribed prophylactic therapy for at least 6 months prior to Screening per Investigator assessment.
- I 07. Willing and able to comply with the study requirements and to provide written informed consent and assent in the case of patients under the age of legal consent, per local and national requirements.

5.2 EXCLUSION CRITERIA

Each patient must not meet any of the following exclusion criteria to be eligible for enrollment in the study (for the United States specific requirements, see [Section 11.6.1.2](#)):

- E 01. Known co-existing bleeding disorders other than hemophilia A or B, ie, Von Willebrand's disease, additional factor deficiencies, or platelet disorders.
- E 02. Current participation in immune tolerance induction therapy (ITI).
- E 03. AT activity $<60\%$ at Screening, as determined by central laboratory measurement.
- E 04. Presence of clinically significant liver disease, or as indicated by any of the conditions below:
- a) INR >1.2 ;
 - b) ALT and/or AST $>1.5\times$ upper limit of normal reference range (ULN);
 - c) Total bilirubin $>ULN$ ($>1.5\times$ ULN in patients with Gilbert's Syndrome);
 - d) History of portal hypertension, esophageal varices, or hepatic encephalopathy;
 - e) Presence of ascites by physical exam.

-
- E 05. Hepatitis C virus antibody positive, except patients with a history of HCV infection who meet both conditions a. and b.:
- a) Completed curative treatment at least 12 weeks prior to enrollment and attained sustained virologic response as documented by a negative HCV RNA at screening, or they have spontaneously cleared infection as documented by negative HCV RNA at Screening.
 - b) No evidence of cirrhosis according to one of the following assessments:
 - FibroScan <12.5 kPa (where available), or
 - FibroTest score <0.75 and APRI <2 (if FibroScan unavailable)
- E 06. Presence of acute hepatitis, ie, hepatitis A, hepatitis E.
- E 07. Presence of acute or chronic hepatitis B infection (IgM anti-HBc antibody positive or HBsAg positive).
- E 08. Platelet count $\leq 100,000/\mu\text{L}$.
- E 09. Presence of acute infection at Screening.
- E 10. Known to be HIV positive with CD4 count <200 cells/ μL .
- E 11. Estimated glomerular filtration rate $\leq 45 \text{ mL/min/1.73 m}^2$ (using the Modification of Diet in Renal Disease [MDRD] formula).
- E 12. Co-existing thrombophilic disorder, as determined by presence of any of the below as identified at central laboratory (or via historical results, where available):
- a) FV Leiden mutation (homozygous or heterozygous)
 - b) Protein S deficiency
 - c) Protein C deficiency
 - d) Prothrombin mutation (G20210A; homozygous and heterozygous)
- E 13. History of antiphospholipid antibody syndrome.
- E 14. History of arterial or venous thromboembolism, atrial fibrillation, significant valvular disease, myocardial infarction, angina, transient ischemic attack, or stroke. Patients who have experienced thrombosis associated with indwelling venous access may be enrolled.
- E 15. Had a malignancy within 2 years, except for basal or squamous cell carcinoma of the skin that has been successfully treated.
- E 16. Any condition (eg, medical concern), which in the opinion of the Investigator, would make the patient unsuitable for dosing on Day 1 or which could interfere with the study compliance, the patient's safety and/or the patient's participation in the completion of the treatment period of the study. This includes significant active and poorly controlled

(unstable) cardiovascular, neurologic, gastrointestinal, endocrine, renal or psychiatric disorders unrelated to hemophilia identified by key laboratory abnormalities or medical history.

- E 17. At Screening, anticipated need of surgery during the study or planned surgery scheduled to occur during the study.
- E 18. Completion of a surgical procedure within 14 days prior to Screening, or currently receiving additional factor concentrate or BPA infusion for postoperative hemostasis.
- E 19. History of multiple drug allergies or history of allergic reaction to an oligonucleotide or GalNAc.
- E 20. Inadequate venous access, as determined by the Investigator, to allow the blood draws required by the study protocol.
- E 21. History of intolerance to SC injection(s).
- E 22. Current or future participation in another clinical study, scheduled to occur during this study, involving an investigational product other than fitusiran or an investigational device; in order to participate in this study, patient must discontinue the investigational product or investigational device at least 30 days (or 5× the investigational product half-life, whichever is longer) prior to dosing (Day 1).
- E 23. Current or prior participation in a gene therapy trial.
- E 24. History of alcohol abuse within the 12 months before Screening. Alcohol abuse is defined as regular weekly intake of more than 14 units (unit: 1 glass of wine [approximately 125 mL] = 1 measure of spirits [approximately 1 fluid ounce] = ½ pint of beer [approximately 284 mL]).

5.3 REMOVAL FROM THERAPY OR ASSESSMENT

Patients or their legal guardian (in case patient is a minor) are free to discontinue treatment or withdraw from the study at any time and for any reason, without penalty to their continuing medical care. Any discontinuation of treatment or withdrawal from the study must be fully documented in the electronic case report form (eCRF) and should be followed up by the Investigator. The Investigator may withdraw a patient at any time if this is considered to be in the patient's best interest.

Patients who discontinue their prophylactic treatment or withdraw consent during the factor or BPA prophylaxis period (BPA prophylaxis period is not applicable for the subgroup of Cohort A patients who are not responding adequately to BPA prophylaxis treatment) will be withdrawn from the study. For the United States specific requirements, see [Section 11.6.1.2](#).

Procedures for discontinuation of study drug and/or withdrawal from the study during the fitusiran treatment period are described in [Section 5.3.1](#) and [Section 5.3.2](#), respectively.

5.3.1 Discontinuation of study drug

The Investigator or designee may discontinue dosing in a patient if the patient:

- Is in significant violation of the protocol
- Is non-adherent to treatment regimen
- Experiences a serious or intolerable AE, a life-threatening bleeding episode, eg, any gastrointestinal hemorrhage or intracranial hemorrhage, or life-threatening thromboembolic event
- Requires a prohibited medication
- More than 1 AT measurement <15% if at a dose of 50 mg Q2M

The Investigator will confer with the Sponsor or study Medical Monitor before discontinuing dosing in the patient.

Patients (or their guardians) may decide to discontinue study drug.

In general, patients who discontinue study drug dosing for any reason will be encouraged to remain on the study to complete the remaining assessments through the end of study so that their experiences are captured in the final analyses. If a patient discontinues dosing due to a serious adverse event (SAE), the SAE should be followed as described in [Section 7.6.6](#). When a patient discontinues study drug dosing, the primary reason must be recorded in the appropriate section of the eCRF. Patients who discontinue study drug but who remain on study may receive treatment consistent with local standard practice for their disease per Investigator judgement, as applicable. Safety will be captured for the entire duration of study for patients who discontinue treatment.

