| Study visit (Month) | Screening | Factor or BPA prophylaxis period ^a | | | | | | Fitusiran treatment period ^b | | | | | | | | | | AT F/U ^{d,e} | |
|---------------------------------------|--------------|--|-------------|-------------|------------|------------|------------|---|-----------|-----------------|-----------|-----------|-----------|------------|------------|-----------------------|----------------|-----------------------|--|
| | | Month -6 | Month -5 | Month -4 | Month -3 | Month -2 | Month -1 | Onset period ^b | | Efficacy period | | | | | | | | | |
| | | | | | | | | Baseline | Month 1 | Month 2 | Month 3 | Month 4 | Month 5 | EOT | | EOS/ET ^{c,d} | | | |
| Study day (±Visit Window) | -228 to -169 | Day -168 | Day -140 ±7 | Day -112 ±7 | Day -84 ±7 | Day -56 ±7 | Day -28 ±7 | Day 1 | Day 15 ±3 | Day 29 ±7 | Day 43 ±3 | Day 57 ±7 | Day 85 ±7 | Day 113 ±7 | Day 141 ±7 | Day 169 ±7 | Day 197 ±7 | Day 225 ±7 | |
| Haemo-QOL/Haem-A-QOL ^g | | X | | | | | | X ^w | | | | | | | | | X ^q | | |
| HAL/pedHAL ^g | | X | | | | | | X ^w | | | | | | | | | X ^q | | |
| TSQM-9 ^g | | X | | | | | | X ^w | | | | | | | | | X ^q | | |
| EQ-5D ^g | | X | | | | | | X ^w | | | | | | | | | X ^q | | |
| Fitusiran Administration (Q2M) | | | | | | | | X | | | | X | | X | | X | | | |
| Perioperative Assessment ^f | | | | | | | | Continuous | | | | | | | | | | | |
| Patient Education Module Training | | X | | | | | | X | | | | | | | | | | | |
| Bleed Management Review ^s | | Review with patient at each visit and contact every 2 weeks (±4 days) between visits | | | | | | | | | | | | | | | | | |
| Bleeding Episodes/eDiary ^t | | Review with patient at each visit and contact every 2 weeks (±4 days) between visits | | | | | | | | | | | | | | | | | |
| Adverse Events ^u | | Continuous | | | | | | | | | | | | | | | | | |
| Concomitant Medications ^v | | Continuous | | | | | | | | | | | | | | | | | |

Table 1 - Schedule of assessments

| Study visit (Month) | Screening | Factor or BPA prophylaxis period ^a | | | | | | Fitusiran treatment period ^b | | | | | | | | | | AT F/U ^{d,e} |
|---------------------|---------------------------------------|---|-------------|-------------|------------|------------|------------|---|-----------|-----------------|-----------|-----------|-----------|------------|------------|------------|-----------------------|-----------------------|

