A change in the fitusiran dosing regimen is being introduced as a risk mitigation measure for vascular thrombotic events. As the risk of vascular thrombotic events is thought to be increased in the setting of low AT activity levels, a reduced dose of 50 mg administered SC once every 2 months has been selected to minimize the occurrence of AT activity levels below 10%. At a reduced dose of 50 mg every 2 months, if a patient has more than 1 AT activity level <15% at any time during fitusiran treatment, the patient will be required to permanently discontinue fitusiran.

Dosing Regimen Simulation

A PK/PD model that describes the dynamics of AT activity for patients treated with fitusiran was developed and characterized on AT activity data from Phase 1 and Phase 2 studies. The model with the estimated parameters was used to simulate AT activity at steady state for different dosing scenarios in a virtual population of 1000 patients.

The results of the simulations are shown in [Table 3](#). Every 2 months (Q2M) and every month (QM) refer to fitusiran dosing every 8 weeks and every 4 weeks respectively; Trough AT and Peak AT are trough and peak AT activities; 5th, Median and 95th referring to 5th percentile, median and 95th percentile.

Table 3 – Simulated AT activity percentiles, for various doses of fitusiran

| REGI MEN | Min AT | TroughAT_ 5th_SS | TroughAT_Me dian_SS | TroughAT_ 95th_SS | Max AT | PeakAT_5 th_SS | PeakAT_Me dian_SS | PeakAT_9 5th_SS |
|-------------|-----------|---------------------|------------------------|----------------------|-----------|-------------------|----------------------|--------------------|
| 50 Q2M | 10.5 | 13.9 | 23.3 | 39.7 | 77.5 | 17.87 | 32.37 | 56.42 |
| 50 QM | 7.96 | 10.3 | 17.2 | 29.6 | 58.5 | 11.36 | 18.23 | 31.15 |

Based on the simulation results from [Table 3](#), starting all patients on a 50 mg Q2M regimen is expected to achieve AT activity above 10% for all patients.

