6.2.3 Dose modifications

Instructions for AT-driven fitusiran regimen modification are provided in [Section 6.2.3.2](#). If an IMP-related AE occurs in a patient that the Investigator judges as presenting a potential risk to the patient for further dosing, the fitusiran dose may be held at the discretion of the Investigator and the study Medical Monitor should be contacted.

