6.2.3.2 Antithrombin level criteria for a dose adjustment

With amendment 6, patients will resume dosing at a dose of 50 mg Q2M ([Table 1](#)). Patients rolling over from this study to the extension study may have the option for dose escalation in that study if dose escalation criteria defined in that protocol are met.

Upon the first AT level <15%, the patient must have another AT activity level sample drawn within 1 week of site receipt of the result. If this result is <15%, this will be considered the second AT activity level <15%. Patients receiving fitusiran at a dose of 50 mg Q2M with more than 1 AT activity level <15% at any time during the study must permanently discontinue fitusiran.

See the rationale for a new dosing justification in [Section 1.4](#).

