Procedures for discontinuation of study drug and/or withdrawal from the study during the fitusiran treatment period are described in Section 5.3.1 and Section 5.3.2, respectively.

Section 6.3.1 ~~Factor Concentrates or~~ Bypassing agent prophylaxis

Section 6.3.1.1 Routine use of ~~factor or~~ bypassing agent prophylaxis in the ~~factor or~~ bypassing agent prophylaxis period

During the ~~factor or~~ BPA prophylaxis period, patients will continue to receive prophylaxis with their usual products on a regimen consistent with recommendations in the approved prescribing information, allowing for adjustment to individual patient response, and designed to decrease spontaneous bleeding. The regimen used during the ~~factor or~~ BPA prophylaxis period must have a minimum frequency of administration as presented in Table 4. The subgroup of Cohort A patients who are not responding adequately to BPA prophylaxis treatment will not participate in this BPA prophylaxis period and will directly start the fitusiran treatment period after the screening period.

Table 15 - ~~Factor or~~ Bypassing agent prophylaxis requirements

| Type of Factor or BPA replacement | Frequency of administration |
|--|-----------------------------|
| Standard half life FVIII | Twice weekly |
| Extended half life FVIII | Once weekly |
| Standard half life FIX | Once weekly |
| Extended half life FIX | Once biweekly |
| aPCC | Twice weekly |
| rFVIIa | Every other day |

Abbreviation: aPCC= activated prothrombin complex concentrates; BPA=bypassing agent; FVIII = ~~Factor VIII~~; FIX = ~~Factor IX~~; rFVIIa=recombinant Factor VIIa

Section 6.3.1.2 Management of ~~factor or~~ bypassing agent prophylaxis during the transition to the fitusiran treatment period

The first 28 days of fitusiran treatment is referred to as the onset period. During the onset period AT lowering will be progressing toward therapeutic levels. Patients will continue ~~factor or~~ BPA prophylaxis with minimum frequency as in Table 4, for the first 7 days of the fitusiran onset period. Subsequent to Day 7 of the fitusiran treatment period, ~~factor concentrates or~~ BPAs should be administered only for bleeding episodes or if needed in advance of invasive medical procedures.

Section 6.3.2 Management of bleeding episodes

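### Protocol Section 5.3.1 makes stopping after more than one AT value below 15% on 50 mg Q2M optional, while Sections 1.4 and 6.2.3.2 make it mandatory and permanent

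*Protocol*

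**What the plan says.** Three sections of the current protocol (amendment 06) deal with a patient on 50 mg every 2 months who has more than one antithrombin (AT) value below 15%.

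- **Section 5.3.1 (Discontinuation of study drug).** The list opens with "The Investigator or designee may discontinue dosing in a patient if the patient" and its last item is "More than 1 AT measurement <15% if at a dose of 50 mg Q2M". The section does not say that the stop is permanent and does not refer to Section 6.2.3.2. It asks the investigator to confer with the sponsor or Medical Monitor before stopping.
- **Section 6.2.3.2 (AT criteria for a dose adjustment).** After a first value below 15%, a repeat sample is due within 1 week of the site receiving the result. A second value below 15% completes the trigger. Patients "with more than 1 AT activity level <15% at any time during the study must permanently discontinue fitusiran".
- **Section 1.4 (Dose rationale).** On the same trigger, "the patient will be required to permanently discontinue fitusiran".

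Two cross-references bear on which text a site will use. Section 5.3 states: "Procedures for discontinuation of study drug and/or withdrawal from the study during the fitusiran treatment period are described in" Sections 5.3.1 and 5.3.2, the first covering study-drug discontinuation. The US version of Section 5.3, in Section 11.6.1.2, repeats this. Section 6.2.3 points the other way for AT-driven changes: "Instructions for AT-driven fitusiran regimen modification are provided in" Section 6.2.3.2.

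**The concern.** A stopping rule should carry the same force wherever it appears. Here the section named for stopping study drug presents as discretionary what the dosing section presents as compulsory. A site working from Section 5.3.1 alone could keep dosing a patient who has to stop.

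Section 1.4 introduces the 50 mg Q2M regimen and its AT rule as mitigation for vascular thrombotic events. Section 1.2.2.2 lists serious vascular thrombosis as an identified risk and reports one death in a patient with cerebral venous thrombosis. The stake is therefore patient safety and trial conduct, not the estimate of treatment effect.

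**Working it through.** The point is one of wording, so the main check is a comparison of the texts.

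| | Section 5.3.1 | Section 6.2.3.2 | Section 1.4 |
|---|---|---|---|
| Regimen | 50 mg Q2M | 50 mg Q2M | 50 mg every 2 months |
| Trigger | more than 1 AT <15% | more than 1 AT <15% | more than 1 AT <15% |
| Force | may | must | required |
| Stated to be permanent | no | yes | yes |
| Refers to 6.2.3.2 | no | – | no |

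**Is the difference resolved elsewhere?** No. The US and Japan appendices do not amend Section 5.3.1. Table 1 footnote n requires the repeat sample but states no consequence. The consultation step in 5.3.1 applies before stopping. No contact is required of an investigator who decides to continue, so the step would not catch the error that matters.

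**Upper bound on extra doses.** Table 1 schedules fitusiran on Days 1, 57, 113 and 169, which is 4 doses. AT samples are scheduled on Days 15, 29 and 43, and the repeat is due within 1 week of the site receiving a low result. Two values below 15% can therefore be on record before Day 57. The most that could follow is 4 − 1 = 3 doses (Days 57, 113 and 169).

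**Are values below 15% plausible?** Table 3 gives a simulated 5th-percentile steady-state trough of 13.9 at 50 mg Q2M. Since 13.9 < 15, at least 5% of simulated patients have a steady-state trough below 15%, with no distributional assumption. In the virtual population of 1000 that is at least 0.05 × 1000 = 50 patients.

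These two figures describe different situations. The three-dose bound concerns a patient who triggers after one dose, and the 13.9 is a steady-state value. The second shows only that single low values are to be expected. The documents do not allow an estimate of how often two measured values would fall below 15%.

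**Numbers exposed.** SAP Section 2.4 reports only 2 participants on 50 mg Q2M, with their data mainly listed. It does not say whether either met the trigger.

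**The case against.** The strongest reply is that the mandatory rule is already clear. It stands in the operative dosing section, in the dose rationale and in the summary of changes at the front of amendment 06, and Section 6.2.3 directs sites to it. The amendment 05 history even says that the item was added to 5.3.1 to align it with the AT instructions. Section 5.3.1 is also not a complete list of stopping rules: the compulsory liver stops in Section 6.2.3.1 do not appear there. The two texts can both be obeyed, since a site that stops satisfies both, and a site that continues breaches an explicit requirement in 6.2.3.2. Few patients are on the regimen, a patient resuming part-way through the fitusiran period may have fewer than four doses left, and the study was near its end.

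Much of this stands. The intent is not in doubt, the number of patients is small, and three doses is an upper bound. The issue is an internal inconsistency, not a questionable design decision.

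It does not make the wording of 5.3.1 correct. The comparison with the liver rules cuts the other way as well: those stops are left out of the discretionary list, whereas the AT stop is placed in it and so reads as optional. The item does not fit the grammar of the list's opening, which suggests that it was appended without adjusting the stem. The section that holds the mandatory rule is titled as a dose adjustment, so a reader looking for stopping rules would not naturally start there.

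**Conclusion.** The concern holds. Section 5.3.1 states in permissive form a stop that Sections 1.4 and 6.2.3.2 make mandatory and permanent on the same trigger, and nothing in the current text reconciles them. The sponsor should correct it on safety grounds.

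Its reach is limited: at most 3 further doses for a patient on the full Table 1 schedule who triggers after the first dose, and 2 participants on the regimen according to the SAP. Harm would require a site to act on 5.3.1 while overlooking 6.2.3.2, and the documents do not show that this happened. The consequence for the efficacy and safety analyses is negligible, because these focus on participants treated with 80 mg monthly.

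**What to change.** Remove the AT item from the discretionary list in Section 5.3.1 and replace it with a separate sentence, for example:

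> For a patient on 50 mg Q2M, a second AT activity level below 15% requires that fitusiran be stopped permanently (see Section 6.2.3.2, including the repeat sample due within 1 week).

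Placing it after the consultation sentence would avoid the impression that the stop depends on that discussion.

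The cost is one sentence in the next amendment. If patients are still being dosed at 50 mg Q2M, a clarification letter to sites can carry the same sentence. Data collection, sample size and analyses are unaffected.
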